6.3 Randomisation

Subjects will be randomised in a 1:1 ratio to receive LEO 90100 or vehicle twice weekly during the maintenance phase. Randomisation will be stratified by trial site, HPA axis testing, and by baseline disease severity (mild, moderate, severe).

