11.1 Determination of Sample Size

For subjects with psoriasis vulgaris, the number of relapses per year is assumed to be between 4 and 8. We assume that the time to event (first relapse) is a Poisson process, i.e. that events occur continuously and independently at a constant rate. Then the time between events is given by the exponential distribution. Time to event is analysed by means of the hazard function, which can be thought of as the probability of experiencing an event now if you have not experienced one already. [Table 16](#) shows the mean and median waiting times as well as hazards according to number of relapses per year.

Table 16: Mean and median waiting times and hazards according to number of relapses per year

	Number of relapses per year		
	4	6	8
Mean waiting time (weeks)	13.00	8.67	6.50
Median waiting time (weeks)	9.01	6.01	4.51
Hazard	0.077	0.115	0.154

The drop-out rate observed in a long-term trial with calcipotriol/BDP ointment (MCB 0102 INT) was about 30 % over 52 weeks. Assuming an exponential decline this corresponds to a median waiting time for drop out at about 101 weeks. We assume that the same will be the case in this trial and that between 4 to 8 relapses will occur per year in the vehicle group.

A 30 percent reduction in hazard, i.e. a hazard ratio of 0.7 for active treatment group relative to vehicle group is considered to be of clinical interest.

With the above assumptions it follows using a two sample survival test that for detecting a hazard ratio of 0.7 for active treatment group relative to vehicle group, between 178 and 190 subjects per group are needed in order to obtain a power of 90% for a 5% significance level. Thus, 380 subjects should be randomised.

In previous trials in similar populations, approximately 48% subjects treated with LEO 90100 aerosol foam achieved treatment success after 4 weeks of treatment. Assuming a binomial distribution with 48 % probability of success it is estimated that 832 subjects should be included in the trial in order to have 90 % probability of achieving at least 380 subjects to be randomised.

For the HPA axis testing, the aim is to achieve approximately 25 subjects undergoing HPA axis testing after 52 weeks of exposure.

The total number of subjects treated in the trial should also be sufficient to comply with ICH E1 regarding long-term safety. The aim is to achieve at least 300 subjects with 26 weeks of exposure and at least 100 subjects with 52 weeks of exposure.

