11.3.8 General Principles

All significance tests will be two-sided using the 5% significance level. All confidence intervals will be presented with 95% degree of confidence.

An observed cases approach will be used for tabulations of data by visit (i.e. involving only those subjects who attended each specific visit).

Categorical data will be summarised using the number and percentage of subjects in each category and treatment group. Continuous data will be summarised using the mean, median, standard deviation (SD), minimum and maximum values.

All the analyses specified in the protocol will be reviewed in relation to the blinded data actually obtained and the statistical analysis plan update will be finalised before breaking the randomisation code.

The randomisation is stratified by treatment group, trial site, HPA axis testing and disease severity at baseline as factors. Usually, the statistical analysis of efficacy parameters takes all the stratification factors into account. However, the HPA axis test is a safety parameter, which is only determined at a small subset of sites and subjects. Hence stratification by HPA axis test is not applicable for all sites. Also, it is expected that two subjects per site will be randomised. This means that a statistical model having HPA axis testing as a factor may not converge, depending on whether subjects participating in the HPA axis test drop out. Furthermore, the inclusion criteria for participating in the HPA axis test are “Moderate” or “Severe” in the baseline PGA assessment and a baseline BSA between 10 and 30%. Including the stratification factor HPA axis testing would therefore introduce a confounding with the

stratification according to baseline PGA as well as sites. Therefore the stratification according to HPA axis testing is not included in the statistical analyses.

Any changes from the statistical analysis planned in this clinical trial protocol will be described and justified in a protocol amendment/the statistical analysis plan update and/or in the clinical trial report dependent on the type of deviation.

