Statistical methods	
Primary endpoint
 
The primary endpoint is time to first relapse during the maintenance period where relapse is an exacerbation of psoriasis defined as a PGA of at least 'mild'. This will be calculated as the number of days from randomisation to the day where the subject has the first relapse confirmed. For subjects who either do not encounter a relapse or are withdrawn from the trial, the number of days will be treated as a censored observation at the day of end of trial visit.
 
The number of censored and uncensored observations, i.e. number of subjects without relapse and number of subjects with relapse, will be summarised by treatment group. The time to first relapse will be summarised by treatment group for uncensored observations, i.e. subjects with relapse.
 
The primary endpoint will be compared between treatments with the null hypothesis that they are equal against the alternative that they are different. The analysis will be performed both for the full analysis set (primary) and for the per protocol analysis set (supportive). The comparison will be done using a proportional hazards model with treatment group, trial site, HPA axis testing, and severity at baseline (as determined by the PGA) as factors. The estimate of the hazard ratio of active treatment group relative to vehicle group together with the 95% confidence interval and p-value will be presented.
 
The estimated survival curves with confidence intervals will be presented graphically for each of the treatment groups. Moreover the percentiles of the survival distribution will be tabulated by treatment group. The proportion of subjects who are still at risk for a first relapse will be compared between the two treatment groups 24 and 52 weeks after randomisation.
 
Secondary endpoints
 
The secondary endpoints will be analysed for the full analysis set, with the analysis for the per protocol analysis set being supportive. Adjustment for multiplicity will be done using the Holm-Bonferroni

---------------------	--

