5.4.1 Primary Efficacy Endpoint

The primary endpoint will be analysed using a cox proportional hazards model with treatment group, pooled sites, and disease severity at maintenance baseline (as determined by the PGA) as factors. Maintenance baseline is used in the model as compared to baseline at visit 1. See section [5.7](#) for details regarding changes as compared to the protocol.

The survival curves will be estimated using the Kaplan-Meier estimator. A log-log transformation will be applied to the survival function to obtain the pointwise confidence intervals in addition to the confidence intervals for the percentiles of the estimated survival times. The estimated survival curves and the confidence limits will be shown graphically. The percentiles of the estimated survival distribution and 95% confidence limits for the percentiles will be tabulated by treatment group.

Number of subjects still at risk of first relapse at timepoints for scheduled visits will be summarised by treatment group.

Further details for tables, figures and listings for the primary endpoint are given in [Appendix I](#) and [Appendix II](#).

Sensitivity analysis:

In the sensitivity analysis the primary endpoint will be analysed incorporating interval censoring. We will consider three different types of censoring. Subjects who do not encounter a relapse during the trial and subjects who are withdrawn from the trial in the maintenance phase before having a relapse will be right-censored, and the number of days will be treated as a censored observation at the end date of the maintenance phase. Subjects who are confirmed to have a relapse at a scheduled visit are interval censored, and it is assumed that the start of the relapse is between the scheduled visit where the relapse is confirmed and the previous visit where PGA was measured for the subject. For subjects who are confirmed to have a relapse at an unscheduled visit, it is assumed that the relapse starts on the day of this visit. These subjects are assumed to have exact observations. More details are given in [Table 3](#).

The number of subjects without relapse, the number of subjects with relapse confirmed at a scheduled visit, and the number of subjects with relapse confirmed at an unscheduled visit will be summarised by treatment group.

Table 3: Censoring in the sensitivity analysis of primary endpoint

Relapse information	Censoring type	Observation type	Lower endpoint	Upper endpoint

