5.6 General Principles

5.6.1 Pooling of Trial Sites

As many centres randomises only a few subjects, the centres will be pooled together. For the United States, due to the large geographical area and diverse climatic conditions, centres will be pooled with neighbouring centres based on graphical location and climatic zones to form two pooled centres. The pooling of sites is shown in [Table 8](#).

Table 8: Pooling of trial sites

Country	Number of subjects randomised	Pooled sites
Canada	132	CAN140, CAN142, CAN143, CAN144, CAN145, CAN146, CAN147, CAN148, CAN149, CAN150, CAN152, CAN154
France	55	FRA160, FRA161, FRA162, FRA165, FRA167
Germany	52	DEU183, DEU185, DEU186, DEU187, DEU188, DEU189, DEU193
Great Britain	68	GBR200, GBR201, GBR202, GBR203, GBR207, GBR209, GBR210

Poland	56	POL220, POL221, POL222, POL224
United States (1)	68	USA103, USA106, USA109, USA112, USA122
United States (2)	114	USA100, USA102, USA104, USA107, USA108, USA110, USA111, USA113, USA115, USA116, USA117, USA118, USA119, USA120, USA121

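### HPA axis testing is a randomisation stratum that protocol 11.3.8 excludes from the efficacy models and Appendix 1 includes; the main reasons for excluding it no longer fit the SAP's models, though the effect of leaving it out is small

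*Protocol*

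**What the plan says.** Protocol 6.3 sets the design: "Randomisation will be stratified by trial site, HPA axis testing, and by baseline disease severity (mild, moderate, severe". Sections 6.1.3 and 10.6 repeat it, and 6.1.3 makes clear that severity means the PGA at Visit 1.

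Protocol 11.3.8 says that efficacy analyses usually take all stratification factors into account, then makes an exception for HPA axis testing on three grounds:
- it is a safety measure done at few sites and in few subjects;
- with about two subjects expected per site, a model containing it may not converge;
- its entry criteria overlap with baseline PGA, and it overlaps with sites.

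The section concludes: "Therefore the stratification according to HPA axis testing is not included in the statistical analyses". The models in 11.3.3.3, 11.3.3.5 and 11.3.3.6 accordingly have no HPA term.

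Appendix 1 of the same version says otherwise for the primary endpoint: "The comparison will be done using a proportional hazards model with treatment group, trial site, HPA axis testing, and severity at baseline". It also lists HPA axis testing in the remission ANOVA and the Poisson model.

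The SAP changes the other two factors. On sites, 5.6.1 says: "As many centres randomises only a few subjects, the centres will be pooled together". On severity, 5.4.1 says: "Maintenance baseline is used in the model as compared to baseline at visit 1"; 5.4.2.2 makes the same switch for the relapse counts. No SAP efficacy model has an HPA term, and the list of changes in 5.7 does not return to the question.

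**The concern.** Two things are wrong. First, current passages of one protocol state different models for every confirmatory endpoint. Second, the argument in 11.3.8 was written for models with individual sites and Visit 1 PGA, whereas the SAP fits pooled sites and, in most models, Visit 2 PGA. The stated norm of analysing by the strata is therefore set aside for reasons that largely belong to models no longer being fitted.

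HPA subjects must have at least moderate PGA and 10 to 30% BSA at Visit 1 (inclusion criterion 12). The factor therefore carries some information on disease extent, which no other term in the SAP's primary and secondary models does. If it is prognostic, leaving it out of a Cox model pulls the hazard ratio slightly towards 1 and costs some power.

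**Working it through.** **1. The plan's own sample size.** Inputs from protocol 11.1: "A 30 percent reduction in hazard, i.e. a hazard ratio of 0.7 for active treatment group relative to vehicle group", 90% power, 4 to 8 vehicle relapses a year, 30% drop-out over 52 weeks. From 11.3.8: "All significance tests will be two-sided using the 5% significance level". From 6.3: "Subjects will be randomised in a 1:1 ratio to receive LEO 90100 or vehicle twice weekly during the maintenance phase".

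- Events (Schoenfeld): 4(1.960 + 1.282)² / (ln 0.7)² = 331. Freedman gives 338.
- Drop-out hazard: μ = −ln(0.7)/52 = 0.00686 per week.
- Event probability: λ/(λ+μ) × (1 − exp(−52(λ+μ))). At 4 a year, the mean over arms is 0.878.
- Per group: 331/0.878/2 = 189 at 4 a year and 175 at 8 a year (Freedman 193 and 179).

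The plan's 178 to 190 is reproduced. With 380 randomised, power is 90.3% to 92.3%.

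**2. Each reason in 11.3.8 against the SAP models.**

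- *Convergence.* SAP Table 8: 132 + 55 + 52 + 68 + 56 + 68 + 114 = 545 subjects at 55 sites, in 7 pools of 52 to 132. A yes/no HPA term costs one parameter. The reason falls.
- *Overlap with baseline PGA.* Visit 1 PGA is no longer in the Cox model (5.4.1) or the count models (5.4.2.2). For the remission ANOVA, SAP 5.4.2.1 still points to protocol 11.3.3.5, and its entry in 5.7 lists no covariate change; only the Shell 27 footnote names maintenance baseline.
- *Overlap with sites or PGA as confounding.* These are all pre-randomisation variables. Correlation among them widens the intervals for their own coefficients; it does not confound the randomised treatment contrast.
- *Safety test in a small subset.* Still true. It does not prevent the term: subjects not tested are coded no, and the coefficient is estimable if any pool contains both kinds of subject.

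**3. Size for the Cox model, by simulation.** The documents give neither the number randomised with HPA testing nor its prognostic strength. Assumed: 25 or 60 HPA subjects, placed in the US, French and Polish pools; HPA hazard ratio 1 to 3; true treatment hazard ratio 0.7; 4 vehicle relapses a year; 1:1 blocks within pool by HPA status; Cox model with treatment and 7 pools, with and without HPA. There were 1,500 runs per row at N = 380.

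| HPA subjects | HPA hazard ratio | Power, omitted | Power, included | HR, omitted | HR, included |
|---|---|---|---|---|---|
| 25 | 1 | 89.6% | 90.1% | 0.6983 | 0.6975 |
| 25 | 1.5 | 90.1% | 90.5% | 0.6957 | 0.6936 |
| 25 | 2 | 88.5% | 89.6% | 0.6996 | 0.6954 |
| 25 | 3 | 90.1% | 91.1% | 0.7034 | 0.6961 |
| 60 | 1 | 90.7% | 91.3% | 0.6933 | 0.6923 |
| 60 | 1.5 | 88.9% | 89.2% | 0.6999 | 0.6967 |
| 60 | 2 | 88.9% | 90.5% | 0.7039 | 0.6955 |
| 60 | 3 | 87.4% | 90.3% | 0.7109 | 0.6944 |

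Simulation error is about 0.8 points on each power figure. No real gain is possible at HPA hazard ratio 1, so roughly half a point of each difference should be disregarded. Every fit with the HPA term converged.

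- At N = 545 with 30 HPA subjects (5.5%) and HPA hazard ratio 2 (1,000 runs): 97.2% omitted, 97.3% included.
- Under no treatment effect, with 60 HPA subjects and HPA hazard ratio 2 (2,500 runs, N = 380): rejection 5.0% omitted, 5.4% included, with a standard error of about 0.4 points.

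**4. The relapse rate ratio.** Under a log link, a covariate balanced by randomisation can be left out almost without effect. Take 6 vehicle relapses a year, true ratio 0.70, 12% HPA subjects at twice the rate, and 4 weeks of rescue per relapse excluded from risk time. The fraction of time at risk is 1/(1 + 4λ). The crude weekly rates are 0.1262 on vehicle and 0.0887 on active, a ratio of 0.703. Over 8 to 12% HPA subjects and 1.5 to 2.0 times the rate, the ratio is 0.701 to 0.703. No attenuation is claimed here.

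**The case against.** The exclusion was deliberate. It is argued in 11.3.8, and the amendment history shows that it came in with a substantial amendment. The SAP text and Shells 23, 27 and 29 all omit HPA axis testing, so there is little doubt about what will be run. On this view Appendix 1 is simply a summary that was not updated. That stands, and it is the main reason for the low severity. It does not dispose of the contradiction, because both passages are current.

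HPA status is also a weak proxy for extent. It requires separate consent and an assigned site, so subjects with the same BSA elsewhere count as untested, and everyone in the full analysis set was clear or almost clear at randomisation. The assumed hazard ratios have no source in the documents. This is fair: the gain may be close to nil. The case for the term rests on the protocol's own norm of analysing by the strata and on its cost of one parameter.

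A reader might infer that the SAP's changes removed every reason in 11.3.8. They did not: the small-subset reason is untouched, partial overlap with sites remains, and the PGA point is settled for the ANOVA only through Shell 27.

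**Conclusion.** The point holds as a contradiction between current protocol passages together with a partly outdated justification. HPA axis testing could enter the SAP models at no practical cost, and none of the reasons in 11.3.8 now prevents it.

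The consequence of leaving it out is small and conservative: about 0 to 3 points of power at N = 380, with the top of that range needing 60 HPA subjects at a threefold hazard. The hazard ratio shifts by at most about 0.017 (0.711 against 0.694). At the 545 actually randomised, the difference is about 0.1 points in the one scenario run. These figures rest on the assumed subset sizes, hazard ratios and pool placement, and on a Cox model without a severity term. The ANOVA was not simulated.

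Two stronger readings are tempting and unsupported. One is that the primary result is at risk or the type I error inflated; the rejection rate with the factor omitted was 5.0%. The other is that every effect estimate is pulled towards the null; the Poisson rate ratio is essentially unchanged.

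**What to change.** Before unblinding, add HPA axis testing (yes/no, untested coded no) to the Cox model in SAP 5.4.1 and its interval-censored version, the ANOVA in 5.4.2.1, and the Poisson and negative binomial models in 5.4.2.2. Revise the rationale in protocol 11.3.8 so that it agrees with Appendix 1, and record the change in SAP 5.7. Write the ANOVA covariates into the text of 5.4.2.1, so that they do not depend on a shell footnote.

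At minimum, make Appendix 1 and 11.3.8 state the same model, restate the HPA rationale for pooled sites, and pre-specify a sensitivity analysis adjusting for all randomisation factors: site or pool, HPA axis testing and Visit 1 PGA. That would also cover the fact that no randomisation factor enters the SAP Cox model in the form used to randomise.

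The cost is one model term or one extra analysis, plus wording. No new data are needed.

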11.3.9 Handling of Missing Values

In the analysis of the primary endpoint, time to first relapse, missing data are treated as censored observations.

For number of days in remission in the primary analysis a subject is considered not to be in remission from when the subject leaves the trial. Two sensitivity analyses with different imputation as detailed in section [11.3.3.5](#) are performed.

For the secondary endpoint “number of relapses”, subjects only contribute with information until they leave the trial.

There is no imputation of missing data for the exploratory analyses of efficacy and the analyses of patient-reported outcomes.

12 Trial Committees

12.1 Adjudication Committee

A panel of 2 dermatologists and one endocrinologist (“Adjudication Panel”) will review all treatment-emergent AEs to identify AEs of concern associated with long-term use of topical corticosteroids where a causal relationship between the trial medication and the event is at least a reasonable possibility.

The Adjudication Panel will not review AEs which occurred prior to application of the first dose of IP; this includes AEs reported by screening failures (who per definition did not start open-label treatment).

The Adjudication Panel Members (APM) will be independent of the trial (i.e. they will not be participating (sub)investigators) and of LEO (i.e. they will not be LEO employees). They will also be blinded to treatment allocation at the time of the review.

A listing of AEs will be provided to the APM consisting of the following data:

- AE reported Term (as reported in eCRF).
- The MedDRA Preferred Term as coded by LEO.
- The (sub)investigator assessment of causal relationship of the use of trial medication to the event, location of cutaneous events, severity, and seriousness.
- The (sub)investigator assessment of causal relationship of long-term use of corticosteroids to the event. For such AEs of concern, the narrative recorded in the eCRF will also be provided.
- The date of onset, the outcome, and date of outcome.
- The action taken with trial medication.

The listing will be generated for patients with complete data (i.e. source data verification (SDV) and SAE reconciliation have been performed). Several listings will be generated during the trial and adjudications performed on batches of 'complete' patients, until all patients are included in this process.

The APM will be able to request eCRF pages and SAE reports on a per subject basis, should this be required for adjudication purposes.

Each APM will perform the adjudication independently of the other APMs and of LEO. If there is any discrepancies in the events identified by each APM, the APMs will discuss these, either by telephone or in a meeting. If a consensus opinion of all three APMs on identified events is not reached, a conservative approach will be used by including events adjudicated to be related to trial medication by any APM, even if identified by just one of the APMs.

The Clinical Project Manager (CPM)/National Lead Clinical Research Associate (NLCRA) is present at the time of adjudication to provide administrative support only; The CPM/NLCRA will not make any comments in relation to the adjudication of the AEs.

13 Case Report Forms and Data Handling

13.1 Case Report Forms (CRFs)

Data will be collected by means of Electronic Data Capture (EDC). The investigator or staff authorised by the investigator will enter subject data into eCRFs. Data recorded in the eCRFs will be accessible to the trial site and LEO personnel immediately after entry. The eCRFs must be maintained in an up-to-date state at the trial site at all times.

The investigator must verify the correctness of the data entered by the site by electronically date and sign all eCRFs used. This signature information will be kept in the audit trail and

cannot be altered. Any correction(s) made by the (sub)investigator or authorised site staff to the eCRF after original entry will be documented in the audit trail. Changes to data already approved will require the re-signature by the investigator. The person making the change to the data, and the date, time and reason for the change will be identified in the audit trail.

For archiving purposes, each investigator will be supplied with a copy of the eCRFs for all subjects enrolled at the trial site. This is done after completion of the trial and before access to the eCRF is revoked. Audit trail information will be included. eCRFs must be available for inspection by authorised representatives from LEO, from regulatory authorities and/or IEC/IRBs.

